4.1.1 Part 1 (Dose Escalation)

Approximately 30 patients with any solid tumor who require low-dose EBRT will be enrolled sequentially to the four planned NOX66 dose groups (Dose Cohort 1: 800 mg [3 to 6 patients]; Dose Cohort 2: 1200 mg; Dose Cohort 3: 1600 mg; Dose Cohort 4: 2400 mg [3 to 8 patients in each of Dose Cohorts 2 to 4]; total daily dose administered twice a day [BID]). At least 2 patients enrolled in Dose Cohorts 2 to 4 must have mCRPC.

The proposed dose regimen for Part 1 is given in Table 4-1. No intra-subject dose escalation is allowed.

	Dose Cohort					
	1	2	3	4		
Total daily dose	800 mg	1200 mg	1600 mg	2400 mg		
Dosing regimen	400 mg BID	600 mg BID	800 mg BID	1200 mg BID		
Number of suppositories per day	$2 \times 400 \text{ mg}$	2 × 600 mg	$4 \times 400 \text{ mg}$	4 × 600 mg		

Table 4-1Proposed Doses for NOX66 (Part 1)

BID = twice daily

All patients will be closely monitored for any dose-limiting toxicities (DLTs) up to Day 21 of Cycle 1.

Dose escalation will be based on an adapted "3+3" design, where dose cohorts will be expanded for up to 6 patients (Dose Cohort 1) in the event of DLT or up to 8 patients (Dose Cohorts 2 to 4) to allow for robust estimation of PK parameters after being deemed "safe" based on the traditional "3+3" design.

At each dose level, 3 patients will initially be treated with NOX66.

- If none of the first 3 patients enrolled in Cohort 1 experience a DLT during the first treatment cycle, the dose will be escalated to the next level.
- If none of the first 3 patients experience a DLT during the first treatment cycle of Cohorts 2 to 4, then the dose level will be deemed "safe" and up to 5 additional patients will be enrolled to the current dose level for estimation of PK parameters. At the same time (with the exception of Cohort 4), the next dose level will be initiated and the first 3 patients will be enrolled to the escalated dose.
- If 1/3 patients experience a DLT, an additional 3 patients will be enrolled. If 1/6 patients experience a DLT then this dose level will be deemed "safe" and, for Cohorts 2 to 4, 2 more patients may be enrolled for estimation of PK parameters. At the same time, the next dose level will be initiated and the first 3 patients will be enrolled to the escalated dose.
- If > 1/3 or > 1/6 patients experience a DLT, then dose escalation will be halted, and the previous dose will be declared as the MTD.

If the 1200 mg dose is not tolerable (i.e., 2 or more patients with DLTs), an additional 3 patients will be enrolled in the 800 mg dose cohort in order to declare 800 mg as the MTD (if no more than 1/6 patients experience a DLT).

If no DLT is observed at 2400 mg (Dose Cohort 4), dose escalation will be stopped. The proposed highest dose level (2400 mg) will be declared the RP2D.

There will be a temporary halt for enrollment after the first 3 patients are enrolled in each cohort until the SSC clears that the dose level is safe to continue the dose escalation. During the SSC meeting for NOX66 dose escalation decision, the safety and tolerability of both EBRT doses (8 Gy and 20/25 Gy) will also be evaluated. For details on DLT evaluation, see Section 7.1.2.2.

DLT monitoring will be applicable for all patients enrolled in each cohort, including patients enrolled for the purpose of PK analysis; as well as the decision rule for the additional PK patients (i.e., stopping dose escalation).

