2.3.3 Overall Benefit: Risk Conclusion

Considering the measures taken to minimize risk to patients participating in this study, the potential risks identified in association with NOX66 are justified by the anticipated benefits that may be afforded to patients with mCRPC and other solid tumors.

3 Objectives and Endpoints

Objectives	Endpoints				
Primary Objectives and Endpoints					
Part 1 (Dose Escalation):	The primary objective for Part 1 will be determined based on the count of DLTs.				
To determine the MTD and RP2D of NOX66 in combination with low-dose EBRT in patients with any	• MTD is defined as the dose level at which no more than 1 patient out of 6 experiences a DLT at the end of Cycle 1.				
solid tumor	• RP2D is the highest dose administered at which no more than 1 patient out of 6 experiences a DLT at the end of Cycle 1 and the dosage form, including the dosing frequency, is acceptable to patients.				

Table 3-1Objectives and Endpoints

Objectives	Endpoints
 Part 2 (Dose Expansion): Arm 1: To evaluate the effect of NOX66 on PSA response in patients with mCRPC. Arm 2: To evaluate the effect of NOX66 on DCR in patients with BC and NSCLC. 	 PSA response is defined as the proportion of patients with a reduction in PSA in plasma (ng/mL) of ≥ 30% from baseline at the end of Cycles 3 and 6. DCR is measured by the percentage of patients with a best overall confirmed response of CR or PR and SD.
Secondary	V Objectives and Endpoints
Characterize the safety and tolerability of NOX66	Safety and tolerability of NOX66 as determined by AEs, TEAEs, clinical laboratory evaluations, vital signs, 12-lead ECG and physical examinations.
Evaluate the safety and tolerability of both doses of EBRT	Safety and tolerability of both doses of EBRT as determined by AEs, TEAEs, clinical laboratory evaluations, vital signs, 12-lead ECG and physical examinations.
Evaluate the exposure of idronoxil	Concentration of idronoxil and selected metabolites in plasma and derived PK parameters, including but not limited to: C _{max} , T _{max} , AUC _(0-t) , AUC ₍₀₋₆₎ , AUC ₍₀₋₁₂₎ , AUC _(0-inf) , C _{min} and t ₂ , as data permit.

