7.1.2.1 Safety Steering Committee

The safety of the patients enrolled in this study will be closely monitored on an ongoing basis by an SSC during dose escalation review meetings. The SSC will review clinical data from the study, including safety, available efficacy and PK data (if available), and will ensure the appropriate selection of doses to be used in the dose escalation and dose expansion phases of the study. All safety data collected up to Cycle 1 Day 21 for each patient will be reviewed.

The SSC will consist of:

- The Sponsor's Study Team Physician or a designee.
- Clinical Research Organization's Medical Monitor, who will chair the committee.
- The Investigators or a designee from every participating site, at least from sites which enroll patients in the respective dose cohort.
- Other Sponsor and Parexel team members.

The SSC charter will define the exact membership and who should be present for recommendations to be made.

For the initiation of a new dose level, the SSC will evaluate the available safety, tolerability and PK data (if available) of NOX66 in combination with EBRT. Once 3 patients have completed their DLT assessment period, the SSC will review and assess all available safety data to make recommendations regarding that dose and/or the next dose/study part. The decisions and decision-making regarding the next dose level will be documented and provided to the Investigators prior to dosing of new patients. The final decision regarding dose escalation or dose de-escalation will be made by the SSC.

The SSC will be responsible for the following:

- Assessment of all available safety, tolerability and exposure data during the study.
- Defining patients who have experienced a DLT per protocol definitions of DLT (see Section 7.1.2.2).
- All recommendations regarding dose escalation or dose de-escalation of NOX66. The SSC may recommend proceeding with dose escalation, expand the current dose level with additional patient enrollment or de-escalate the dose to a lower dose level.
- All recommendations regarding modification of NOX66 dosing schedule, if required. The SSC may recommend adjusting the NOX66 dose, dosing frequency or schedule during either Cycle 1 or subsequent cycles. In this situation, the protocol must be amended.
- All recommendations relating to initiation of Part 2 enrollment.
- Recommendation for cessation of dose escalation.

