9.4.6.1 Part 1 (Dose Escalation): Recommended Phase 2 Dose

The primary endpoint for Part 1 (dose escalation) is the number of DLTs, which will be used to estimate the MTD and select the RP2D. This will be determined by the dose level at which no more than 1 patient out of 6 patients experiences a DLT during Cycle 1.

For assessment of DLTs, toxicities will be coded using the Medical Dictionary for Regulatory Activities (MedDRA) v22.0 or higher and graded according to NCI-CTCAE v5.0. See Section 7.1.2.2 for details on DLT criteria.

The number of DLTs experienced by a patient will be summarized by DLT type for each dose cohort and DLT events will be listed by patient. The listing will include the description, severity and relationship of the events to study drug.

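### At 2400 mg, the declaration rule in Section 4.1.1 does not implement the protocol's own definition of MTD and RP2D (at most 1 DLT in 6 patients)

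*Combined protocol and SAP*

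**What the plan says.** **Definitions.** Table 3-1 (Section 3): "MTD is defined as the dose level at which no more than 1 patient out of 6 experiences a DLT". The RP2D is the highest dose meeting the same count, with a further condition: "and the dosage form, including the dosing frequency, is acceptable to patients". Section 9.4.6.1 repeats the count for the primary endpoint: "no more than 1 patient out of 6 patients experiences a DLT during Cycle 1".

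**Declaration rules in Section 4.1.1, repeated in the synopsis (Section 1.1).**
- Cohorts 2 to 4 (1200, 1600 and 2400 mg) may hold 3 to 8 patients. After 0/3 the dose is deemed safe and "up to 5 additional patients will be enrolled to the current dose level for estimation of PK parameters". The next dose level opens in parallel, except for Cohort 4.
- After 1/6 the dose is deemed safe, two more PK patients may be added in Cohorts 2 to 4, and the next dose level opens. This bullet makes no exception for Cohort 4.
- If a dose has more than 1/3 or more than 1/6 with DLTs, the dose below it becomes the MTD. No patient count is required at that lower dose.
- At the top dose the condition is: "If no DLT is observed at 2400 mg (Dose Cohort 4), dose escalation will be stopped". The consequence comes in a separate sentence, again without a patient count: "The proposed highest dose level (2400 mg) will be declared the RP2D".
- A top-up to 6 patients before declaration is written only for 800 mg.
- PK patients are under DLT monitoring and the same decision rule.

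**Committee steps.** "There will be a temporary halt for enrollment after the first 3 patients are enrolled in each cohort until the SSC clears" the dose level. Under Section 7.1.2.1, once 3 patients have completed DLT assessment, the Safety Steering Committee (SSC) may "make recommendations regarding that dose and/or the next dose/study part". Section 7.1.2.2 requires at least 3 evaluable patients per cohort.

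**The concern.** Declaring the MTD and RP2D is the primary objective of Part 1. The RP2D is then given to everyone in Part 2: 40 patients in Arm 1 plus 24 to 30 in Arm 2, so 64 to 70 in all. The committee works from Section 4.1.1, and at 2400 mg that section departs from the definition in both directions:

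- **Too loose.** With no denominator, zero DLTs in three patients satisfies the rule. The acceptability condition is also absent.
- **Too strict, or silent.** One DLT in 6 meets the definition but fails the zero-DLT condition. The 1/6 bullet then points to a dose level above 2400 mg that does not exist.

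The top dose is also the one with least support. In the earlier radiotherapy study (Section 4.2) the highest dose was 1200 mg, given to 15 patients, and that study had no DLTs. Yet the explicit six-patient check is attached to 800 mg only.

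**Working it through.** **Inputs from the documents.** Cohort ranges are 3 to 6 (800 mg) and 3 to 8 (the other three). The Part 1 maximum reproduces: 6 + 3 × 8 = 30. With 3 patients in each cohort the total is 4 × 3 = 12.

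**Assumed input.** The documents give no DLT rate for these doses, so the true rate p is set at 10%, 20%, 33% (1/3), 40% and 50%. Write q = 1 − p. All figures are for 2400 mg, given that it is reached.

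**Step 1: acceptance with nobody enrolled beyond the 3+3 path.**
- A: P(0/3) = q³.
- B: P(1/3, then 0/3) = 3pq² × q³ = 3pq⁵.
- C: chance of being deemed safe = A + B.
- D: the definition, P(at most 1 DLT in 6) = q⁶ + 6pq⁵.
- E: P(2 or more DLTs in 3 further patients) = 3p²q + p³. This is the chance that the definition fails after 0/3.

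| | 10% | 20% | 33% | 40% | 50% |
|---|---|---|---|---|---|
| A: 0/3 (meets the written RP2D rule) | 72.9% | 51.2% | 29.6% | 21.6% | 12.5% |
| B: 1/6 (safe, no declaration) | 17.7% | 19.7% | 13.2% | 9.3% | 4.7% |
| C: A + B | 90.6% | 70.9% | 42.8% | 30.9% | 17.2% |
| D: at most 1/6 | 88.6% | 65.5% | 35.1% | 23.3% | 10.9% |
| E: definition fails after 0/3 | 2.8% | 10.4% | 25.9% | 35.2% | 50.0% |
| C − D = A × E (points) | 2.0 | 5.3 | 7.7 | 7.6 | 6.25 |

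The whole excess comes from stopping at 0/3. Row C treats 1/6 as acceptable, as Table 3-1 does.

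**Step 2: expansion filled to 8, with 2 or more DLTs failing the dose.** Acceptance is P(at most 1 in 8) = q⁸ + 8pq⁷: 81.3%, 50.3%, 19.5%, 10.6% and 3.5%. Each figure is below row D, so a filled cohort is stricter than the definition.

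**Step 3: one DLT in a filled cohort.** P(exactly 1 in 8) = 8pq⁷: 38.3%, 33.6%, 15.6%, 9.0% and 3.1%. This result fails the zero-DLT condition. It is not above 1/6, so it does not fail the dose either, and Section 4.1.1 attaches no declaration to it. Filling the cohort therefore closes the 0/3 gap but not the single-DLT gap.

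**Step 4: precision.** Exact two-sided 95% limits for the DLT rate (for 0/n the upper limit is 1 − 0.025^(1/n)):
- 0/3: 0 to 70.8%
- 0/6: 0 to 45.9%
- 1/6: 0.4% to 64.1%
- 1/8: 0.3% to 52.7%

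**The case against.** The strongest defence is that three patients is not what the drafters had in mind. Section 4.1.1 refers to the first 3 patients where it means three. The 2400 mg sentence refers to Dose Cohort 4, a cohort of 3 to 8. After 0/3 the text says further PK patients will be enrolled, and Cohort 4 is exempted only from opening a next dose. Those PK patients count for DLTs. The 1-in-6 definition stands elsewhere in the protocol, and the SSC can expand a dose level and must advise before Part 2 starts.

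Much of this stands, and it rules out three stronger readings:

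- **That the plan intends to open Part 2 on three patients.** It does not. Three is a permitted minimum; the maximum of 30 shows that expansion is planned. The pause after three patients is a clearance step, and a recommendation on the next study part is allowed there but not required.
- **That 1/6 at 2400 mg has no rule at all.** The 1/6 bullet names Cohorts 2 to 4 and deems the dose safe, and Table 3-1 would accept it as RP2D if the dosage form is acceptable. Only the declaration is missing from Section 4.1.1.
- **That every dose above 800 mg is equally exposed.** The missing six-patient floor also applies in wording when 1200 or 1600 mg becomes the MTD as the dose below a failed one. But their PK expansion runs while the next dose enrolls, so a three-patient declaration is unlikely there, and 1200 mg has the 15 earlier patients behind it.

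The defence does not close the gap at 2400 mg. An upper limit on PK enrollment sets no minimum, and the declaration sentence is mandatory once its condition holds. Expectation and committee discretion do not reconcile two written standards for a primary objective.

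**Conclusion.** The concern holds at 2400 mg as a conflict between Section 4.1.1 (with the synopsis) and the definitions in Table 3-1 and Section 9.4.6.1. Section 4.1.1 can be followed to the letter and declare an RP2D on 0/3 that the definition does not yet support. With a single DLT in 6 to 8 patients it makes no declaration, and the committee must turn to Table 3-1.

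The effect on acceptance is modest: about 2 to 8 percentage points above the definition. That rests on assumed DLT rates of 10% to 50%, on 2400 mg being reached, and on nobody being enrolled beyond the 3+3 path. With expansion to 8 the direction reverses. The point deserves correction because it concerns the Part 1 primary objective and the dose for Part 2, and because the remedy is cheap.

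**What to change.** Make these changes in Section 4.1.1 and the matching synopsis text:

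1. State that no dose is declared MTD or RP2D until at least 6 DLT-evaluable patients have been treated at it, with at most 1 DLT among all evaluable patients at that dose (6 to 8). Use the planned PK slots first.
2. Replace the two 2400 mg sentences with: if condition 1 and the Table 3-1 acceptability condition are both met at 2400 mg, escalation stops and 2400 mg is declared the RP2D. This covers 0 or 1 DLT in 6, 7 or 8 patients.
3. In the 1/6 bullet, exempt Cohort 4 from opening the next dose level, as the 0/3 bullet already does.

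Then align Table 3-1 and Section 9.4.6.1 to at most 1 DLT among at least 6 evaluable patients, so that the definitions and the algorithm agree at 7 and 8 patients too.

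**Cost.** Up to 3 more evaluable patients and one more 21-day DLT window at the declared dose. This normally fits within 8 per cohort and 30 overall, unless more than 2 patients in the cohort are non-evaluable. At most 1 DLT in 7 or 8 is stricter than 1 in 6: at a true rate of 20%, acceptance is 57.7% or 50.3% against 65.5%. That agrees with Section 4.1.1, which calls 1200 mg not tolerable at 2 or more patients with DLTs and puts PK patients under the same rule.

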4.1.2 Part 2 (Dose Expansion)

Part 2 will be expanded to enroll additional patients with mCRPC (Arm 1), BC and NSCLC (Arm 2). All patients will be treated with NOX66 RP2D along with low-dose EBRT (8 Gy or 20/25 Gy given as 1 or 5 fractionated doses, respectively).

Part 2 will enroll 2 treatment arms:

- Arm 1 (n = 40): Patients with mCRPC.
- Arm 2 (n = 24 to 30): Patients with BC and NSCLC.

4.2 Scientific Rationale for Study Design

Better SOC treatments for patients with prostate cancer and patients with other solid tumors, who have exhausted treatments, are needed. Based on the positive results observed in Phase 1 clinical studies with NOX66, further investigation is warranted.

The study is divided into 2 parts: Part 1 (dose escalation) and Part 2 (dose expansion). During Part 1, four dose levels of NOX66 will be examined to determine the MTD and RP2D to be used in further clinical development of NOX66. In Part 2, the confirmed RP2D dose level will be further examined in patients with mCRPC, BC and NSCLC. Part 2 will also examine the effect of NOX66 on PSA of patients with mCRPC and the tumor response in patients with BC and NSCLC.

Radiotherapy (i.e., low-dose EBRT) will be provided to patients during this study. Low-dose EBRT is administered for the treatment of symptomatic lesions and/or to prevent asymptomatic lesions from becoming symptomatic. Low-dose EBRT (8 Gy or 20/25 Gy as 1 or 5 fractionated doses, respectively) will be administered in this study for symptom control of lesions and

prevention of signs and symptoms. The safety of the combination of NOX66 and EBRT has been tested in men with symptomatic mCRPC¹ (see IB² for details).

The starting dose, dose escalation decision points and patient population size are based on accepted methodology for Phase 1/Phase 2 studies.

In the previous study (NOX66-002A), the doses of 400 mg, 600 mg, 800 mg and 1200 mg of NOX66 were explored in combination with low-dose EBRT in patients with mCRPC. The highest dose tested in this study was 1200 mg and a total of 15 patients have been treated with this dose. There were no DLTs reported in that study. Based on the NOX66-002A study safety and efficacy data this planned study is designed to continue the dose escalation from 800 mg (400 mg BID) to 1200 mg (600 mg BID) to 1600 mg (800 mg BID) followed by 2400 mg (1200 mg BID), if tolerable.

In the previous trial, the total duration of NOX66 treatment was up to 16 days and low-dose EBRT of 20 Gy was given in 5 fractionated doses over 5 to 7 days. NOX66 will be administered in this planned study on a 21-day cycle basis (14 days on treatment followed by 7 days off treatment) during Cycle 1, and on a 14-day cycle basis (7 days on treatment followed by 7 days off treatment) from Cycle 2 onwards. NOX66 will be administered until disease progression, unacceptable toxicity, withdrawal of consent, start of a new anticancer therapy, withdrawal of the patient by the Investigator or termination of the study by the Sponsor.

The timings of safety and PK assessments in the study have been designed on the basis of non-clinical and clinical findings. These data will be important to evaluate exposure-response relationships for efficacy and safety in mCRPC and other tumor types.

As part of the clinical drug development program for NOX66, the Sponsor plans to include investigations into PD biomarker profiles and their relation to study drug effect at the intended dosage. These biomarkers will be derived from blood samples taken during the study. There are many potential benefits to this biomarker research, including the possibility to identify patients most likely to benefit from treatment, explain outliers and non-responders or explain adverse reactions related to study drug exposure. This research may result in an understanding of the impact of variation between individuals and how it can be utilized to bring better drug products to the clinic.

4.3 Justification for Dose

The selected starting dose, 800 mg NOX66 (total dose; 400 mg BID), has been used in a previous clinical trial (NOX66-002A) and was shown to be safe and well tolerated. This dose level is the possible lowest BID dose of NOX66.

Low-dose EBRT (8 Gy or 20/25 Gy given as 1 or 5 fractionated doses, respectively) is considered SOC in this patient population. The choice of dose/fraction is at Investigator's discretion based on patient's need. Site will need to follow institutional practice for low-dose EBRT administration.

4.4 End of Study Definition

Once a patient completes or discontinues study drug, he/she will be followed up every 12 weeks $(\pm 2 \text{ weeks})$ after the last dose of study drug for disease progression up to 12 months, and for safety until death or the patient is lost to follow-up.

For the entire study, study completion is defined as the last visit of the last patient for any protocol related activity (last patient, last visit), including telephone contact. For individual patients, study completion is defined as the time of the patient's last data collection.

The study will finish when the last patient enrolled in Part 2 completed 6 months of treatment; all patients receiving study drug at that time will be switched to the NOX66 compassionate access program. Those patients on the compassionate access program will continue to receive NOX66 treatment until disease progression or unacceptable toxicity. These patients will be followed until death, or the patient is lost to follow-up.

5 Study Population

The study population will consist of patients with mCRPC, BC, NSCLC or other solid tumors who have failed at least one line of prior treatment and for whom, according to the Investigator, are eligible for low-dose EBRT for at least one symptomatic or minimally symptomatic lesion (for the prevention of symptoms).

5.1 Inclusion Criteria

Patients are eligible to be included in the study only if all of the following criteria apply:

Informed Consent

1. Patient is capable of giving signed informed consent which includes compliance with the requirements and restrictions listed in the ICF and in this protocol.

Type of Patient and Disease Characteristics

- 2. Patient has a minimum life expectancy of 6 months.
- 3. Patient is 18 years or older at the time of signing the informed consent.
- 4. Histological or cytological confirmation of prostate cancer, BC, NSCLC and any other solid tumors.
- 5. Confirmed metastatic disease by imaging (e.g., bone scans, X-rays, ultrasound, computerized tomography [CT], magnetic resonance imaging [MRI]).
- 6. Documented disease progression (e.g., based on radiographic imaging, PSA or other clinical parameters) following first or later lines of anticancer systemic treatment.
- 7. Patient is eligible for low-dose EBRT for at least one lesion.
- 8. Patients with prior RT are eligible, only if there is no potential for field overlap between the prior RT and the planned RT.
- 9. For patients with BC or NSCLC: Patient must have at least one measurable lesion as per RECIST v1.1 (in Part 2 only).
- 10. Patient has Eastern Cooperative Oncology Group (ECOG) performance status of 0 to 2.
- 11. Adequate bone marrow function defined as:
 - Absolute neutrophil count $\geq 1.5 \times 10^9$ /L.
 - Platelet count $\geq 100 \times 10^9$ /L.
 - Hemoglobin \ge 9.0 g/dL (with or without transfusion).
- 12. Adequate renal function defined as:
 - Creatinine clearance as measured by the Cockcroft-Gault equation > 30 mL/min.

13. Adequate liver function defined as:

- Serum total bilirubin ≤ 1.5 × upper limit of normal (ULN; patients with confirmed Gilbert's syndrome may be included in the study).
- Aspartate aminotransferase (AST)/alanine aminotransferase (ALT) ≤ 2.5 × ULN (or ≤ 5 × ULN in patients with liver metastasis). Elevated alkaline phosphatase is not exclusionary if due to the presence of bone metastasis and liver function is otherwise considered adequate in the Investigator's judgement.

Metastatic Castration-resistant Prostate Cancer

- 14. Baseline testosterone levels \leq 14.4 ng/dL and ongoing medical castration must be maintained throughout the duration of the study.
- 15. Patient has evidence of symptomatic and/or progressive disease. Progressive disease is defined as any one of the following:
 - Radiographic disease progression in soft tissue (nodule or visceral metastasis) and/or bone with or without PSA progression. Objective evidence of increase in radiographic lesions or the appearance of 2 or more new lesions.
 - Prostate-specific antigen progression: At least 3 consecutive rising PSA levels (≥ 2 to 5 ng/mL) separated by at least 1 week, with castrate levels of testosterone.

Breast Cancer Patients

16. Known hormone receptor status (estrogen receptors/progesterone receptors or estrogen receptors alone). Breast cancer patients are allowed to be on background hormonal treatment.

Contraception

Contraceptive use should be consistent with local regulations regarding the methods of contraception for those participating in clinical studies.

NOTE: The reliability of sexual abstinence for male or female enrollment eligibility needs to be evaluated in relation to **the duration of the clinical study and the preferred and usual lifestyle of the patient**. Periodic abstinence (e.g., calendar, ovulation, symptothermal, or post ovulation methods) and withdrawal are not acceptable methods of contraception.

Male Patients:

17. Patient must have had a vasectomy or must agree to use a highly effective contraception as detailed in Section 10.4 of this protocol during the treatment period and for at least 3 months after the last dose of study drug and refrain from donating sperm during this period.

Female Patients:

- 18. A female patient is eligible to participate if she is not pregnant (see Section 10.4), not breastfeeding, and at least one of the following conditions applies:
 - Not a woman of childbearing potential (WOCBP) as defined in Section 10.4.

OR

• A WOCBP who agrees to follow the contraceptive guidance in Section 10.4 and not to donate ova during the treatment period and for at least 3 months after the last dose of study drug.

